## **9.5 Analysis Windows**

Protocol-specified visits and unscheduled clinical visits may be used to capture missed or partially completed clinical visits; therefore, analysis visits and their windows are defined using Study Day (See [Section 9.4.3](#)). For the purposes of data analysis and summary, assessments and

measurements will be preferentially flagged based on the collection date/time that is closest to the protocol-scheduled time point (or target Study Day). Analysis visit windows are presented in **Table 7**.

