Once safety data are available for Cohort 5 and 7 sentinels, the DMC will convene and make a recommendation regarding initiation of pediatric cohorts at doses >200 mg BID. The Sponsor will then decide whether to initiate Cohort 8 at a dose up to 400mg BID. Subsequently, the DMC may review data from 4 sentinels from Cohort 8 and make a recommendation regarding further dose increase in the younger age group. Sponsor may then decide whether to initiate Cohort 9 at a dose up to 400mg BID.

A sparse serial blood sampling approach for PK will also be used in Cohorts 4 to 9 on Day 1 (Visit 2) and Week 2/Day 14 (Visit 3). Blood samples for tildacerfont concentration should be obtained pre-dose and between 0.5 - 1.5 hours and 3 - 5 hours post dosing. At these visits, participants will dose in clinic with a meal at 8 am (± 1 hour).

All participants in Cohorts 4-9 will receive open-label tildacerfont for the 4-week treatment period, after which they may be offered optional continued treatment if the clinical Investigator believes it is in the participant's best interest. Once enrolled in the extension period, participants may adjust tildacerfont dose up to the highest dose recommended by the DMC per age group at the Investigator's discretion.

Table 1. Study Cohorts

Cohort	Age	Corresponding Adult Dose	Subject Numbers	Treatment Duration
1	11- to 17-years	50 mg QD	5	12 Weeks
1a ^a	11- to 17-years	To be determined based on DMC recommendation (50 or 100 mg QD)	5	
2	11- to 17-years	200 mg QD	5	
3	2- to 10-years	50 mg QD, 100 mg QD, OR 200 mg QD	10	
4	≥ 18 -years	200 mg BID	5	4 weeks
5	≥ 18 -years	300 and/or 400 mg BID	5+5 ^c	
6	11- to 17-years	200 mg BID	5	
8 ^b	11- to 17-years	300 and/or 400 mg BID	5+5 ^c	
7	2- to 10-years	200 mg BID	5	
9 ^b	2- to 10-years	300 and/or 400 mg BID	5+5 ^c	
			Up to 70 subjects total	

Abbreviations: BID=twice daily; DMC=Data Monitoring Committee; QD=once daily.

^a Cohort 1a is an optional interim dose cohort that may be enrolled only if needed per DMC recommendation and Sponsor decision, in the event of a safety concern in participants in Cohort 1.

^b Cohort 8 and 9 are adaptive cohorts that may be enrolled based on emerging safety data and per DMC and Sponsor recommendation/approval.

^c+5 allows for the option of dosing 300mg before or after 400 mg Cohort is initiated if indicated by the DMC

A schema of the study design is presented in [Figure 1](#) for Cohorts 1, 1a, 2, and 3; and in [Figure 2](#) for Cohorts 4, 5, 6, 7, 8, and 9.

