3.1.2.6. Visit 6 (EOT for Cohorts 1-3) (Week 12 ±3 days)

Visit 6 will be conducted as an outpatient visit. The following activities will be performed:

- Review concomitant medications for any changes
- Pregnancy test for FOCP (urine)
- Safety labs (see [Appendix 1](#))
- Pharmacodynamics (ACTH, 17-OHP, A4, testosterone, and 11KT) drawn prior to GC dosing at approximately 8 AM (±1 hour). Fasting is not required.
- Cortisol
- Tildacerfont concentration (single sample) drawn prior to GC dosing at approximately 8 AM (±1 hour). Fasting is not required.
- GC dosing adjustments (for Cohort 1-3 patients who are continuing in the EP) to be determined after A4 value is resulted
- Urinalysis
- Vital signs: blood pressure, pulse rate, body temperature, respiration rate, and weight
- Physical exam (full)

- 12-lead ECG
- Suicidality Questionnaire- C-SSRS since last visit (participants aged 6- to 17-years only)
- Depression and Anxiety Questionnaires (PROMIS or SWYC depending on age of participant)
- Study drug accountability
- Assess for AEs

3.1.2.7. Safety Follow-up Visit Telephone Call (30 days after last dose \pm 7 days)

Approximately 30 days after the last dose of study drug (post the 12- or 4-week treatment period, depending on cohort, or post the extension), participants will have a final follow-up visit conducted by telephone. Concomitant medications and AEs will be reviewed. If any ongoing safety issues are identified, the participant may be asked to visit the clinic for additional tests, labs, or assessments.

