3.1.3. Extension Period

Participants who complete the 12- or 4-week treatment period, depending on cohort, may be eligible to continue dosing to complete 2 years on treatment in an extension study. Participants will sign a separate informed consent form at Week 12 or Week 4. Pending DMC review, participants in Cohorts 1 and 1a (if indicated) will receive the adult equivalent dose of 200 mg QD during the extension (i.e., Cohort 1 participants will immediately switch to 200 mg equivalent if the DMC has already recommended this dose for Cohort 2, or participants may enter the extension period on 50 mg equivalent and increase to 200 mg equivalent after such a recommendation is made). If a Cohort 1-3 participant is to dose escalate to the 200 mg equivalent, they may do so at the next scheduled visit or come to the clinic for an unscheduled visit and pick up their new supply of study drug. Participants will receive a follow-up phone call 2 weeks after dose escalation to check for AEs.

Further tildacerfont dose adjustments may occur during the extension on a case-by-case basis at the discretion of the Investigator with Sponsor approval. Any extension participant may receive the highest dose recommended by the DMC for their age group. Dose changes (increase or decrease) may occur at a scheduled visit, an unscheduled visit, or via a phone visit, but any dose escalation > 200mg QD will be followed by safety labs (link to list) within 2-4 weeks of the change. Once all participants are in the extension period, safety- data will be reviewed every 6 months by the DMC. Weight-based dose adjustments may be made at any extension visit, with no follow-up labs required.

For Cohorts 1-3, the first visit of the extension will be Week 12. For Cohorts 4-9, Week 4 will be the first extension visit, followed by extension clinic visits at Weeks 8 and 12 (\pm 2 weeks). Starting at Week 12, all participants will attend clinic visits every 12 weeks (\pm 2 weeks).

Approximately a 12-week supply of study drug, as appropriate, will be dispensed at each visit. Approximately 30 days after the last dose of study drug, participants will have a final follow-up visit conducted by telephone. Concomitant medications and AEs will be reviewed. If any ongoing safety issues are identified, the participant may be asked to visit the clinic for additional tests, labs, or assessments.

The extension study visits will include the following:

- Review concomitant medications for any changes

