## 4 PURPOSE OF THE ANALYSIS PLAN

This statistical analysis plan (SAP) pre-specifies the statistical analysis methods for supporting the completion of a clinical study report (CSR) of Study SPR001-205 for tildacerfont, an investigational drug candidate designed to treat classic congenital adrenal hyperplasia (CAH). This SAP will be used to analyze the safety, efficacy, and pharmacodynamics (PD) data collected during the study. The planned analyses identified in this SAP may be included in regulatory submissions and/or future manuscripts.

The analysis methods described in this plan are considered *a priori*, in that they have been defined prior to clinical database lock. Exploratory analyses that are not defined in this SAP may be performed to support the clinical development program. Any post-hoc or unplanned analyses that are performed for the CSR, but not defined in this SAP, will be documented in the CSR. Changes from the planned analyses are described in [Section 15](#). Should the SAP and the protocol be inconsistent with respect to any further planned analyses, the language of the SAP is governing.

The analysis of pharmacokinetic (PK) concentration data and its parameters will be documented separately. The data analysis for the open label extension period will be covered in a separate SAP.

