**Table 7 Analysis Visit Windows**

Protocol Specified Visit Number	Analysis Visit	Target Study Day	Start (days)	Stop (days)
1	Screening	-15	low	-1
2	Day 1	1	1	8
	Day 2	2		
	Day 8	8		
	Day 14	14		
3	Week 2	15	9	22
4	Week 4	29	23	43
5	Week 8	57	44	71
6	Week 12	85	72	127
7	Week 24	169	128	211
8	Week 36	253	212	295
9	Week 48	337	296	421
10	Week 60	421	341	501
11	Week 72	505	411	599
12	Week 84	589	481	697
13	Week 96	673	551	Last Dose Date + 3 days
7	Follow-up	Last Dose Date + 30		

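### SAP Table 7 assigns Week 4 and Week 12 by study day alone, so an extension or follow-up sample can stand in for an endpoint A4 that was not obtained

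*SAP*

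**What the plan says.** **Windows.** SAP 9.5 defines analysis visits by Study Day and prefers the record nearest the target day. It adds that "Protocol-specified visits and unscheduled clinical visits may be used to capture missed or partially completed clinical visits". In Table 7 the Week 4 row has target 29, start 23 and stop 43. The Week 12 row reads "Week 12 85 72 127" (target, start, stop). Only the Week 96 row is tied to dosing; its stop is "Last Dose Date + 3 days". The Follow-up row has a target of last dose + 30 days and no start or stop.

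**Missing data.** SAP Table 5 and Sections 13.1.1 and 13.1.2 score a missing value at a visit as non-response.

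**Scope.** SAP Section 4 states: "The data analysis for the open label extension period will be covered in a separate SAP". Yet Section 13 points to Table 7 for the visits of the treatment period, and Table 7 runs to Week 96 without separating the cohorts. SAP 13.2.3 summarises biomarker reductions from Week 4 to Week 12, overall and by cohort.

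**What happens after the endpoint visit.** The protocol allows ±3 days for Visit 4 (Week 4) and Visit 6 (Week 12). Under Protocol 3.1.3, pending DMC review, "participants in Cohorts 1 and 1a (if indicated) will receive the adult equivalent dose of 200 mg QD during the extension". For Cohorts 4–9, Protocol 3.1 says: "Once enrolled in the extension period, participants may adjust tildacerfont dose up to the highest dose recommended by the DMC per age group". Participants who do not continue have a safety follow-up 30 ± 7 days after last dose (Protocol 3.1.2.7). It is a telephone call, with PD samples only as needed because of abnormalities at earlier visits (Protocol Table 8, note 2).

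**The concern.** The nearest-to-target rule settles the choice when a usable endpoint sample exists. It does nothing when none exists, which is the case SAP 9.5 has in mind when it lets other visits fill the gap. Any A4 value in the remaining window is then eligible, whatever the participant was taking when it was drawn.

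At stake is the meaning of a response. A participant who should be a non-responder because the endpoint A4 is missing could become a responder on a value obtained under another tildacerfont dose, or after treatment had ended. As-needed follow-up samples are also a selected subset, because they are prompted by earlier abnormalities. By-visit laboratory and vital-sign summaries have the same weakness.

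**Working it through.** **1. Where the stops come from.** They are midpoints between consecutive SAP target days:
- Week 4: (29 + 57)/2 = 43
- Week 12: (85 + 169)/2 = 127

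Both match Table 7. The same rule gives the Week 2, 8, 24 and 36 stops (22, 71, 211, 295). The endpoint rows therefore follow a calendar convention, not a treatment-period rule.

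**2. How far they extend past the planned visit.**
- Week 4: planned Days 25–31 (28 ± 3). The window has 43 − 23 + 1 = 21 days, of which 12 (Days 32–43) come after the planned visit.
- Week 12: planned Days 81–87 (84 ± 3). The window has 127 − 72 + 1 = 56 days, of which 40 (Days 88–127) come after it.

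**3. Extension route.** Protocol 3.1.2.9 defines completion of the treatment period as completing Visit 6 or Visit 4, and Protocol 3.1.3 requires completion for extension entry. The case is therefore an attended visit without a usable A4.
- Cohort 1: if the DMC has already recommended the higher dose, the participant moves from the 50 mg to the 200 mg QD equivalent at Week 12. With the switch on Day 84, an unscheduled A4 on any of Days 85–127 would be labelled Week 12.
- Cohorts 4–9: the extension begins at Week 4, and an unscheduled A4 up to Day 43 would be labelled Week 4.

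Scheduled extension visits add little. The Week 24 visit (168 ± 14 = Days 154–182) cannot reach the Week 12 window. The Cohort 4–9 Week 8 visit (56 ± 14 = Days 42–70) meets the Week 4 window only on Days 42–43.

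**4. Follow-up route, after planned end of treatment.**
- Cohorts 1–3: last dose about Day 84. 84 + 23 = 107 and 84 + 37 = 121. All of Days 107–121 lie inside 72–127.
- Cohorts 4–9: last dose about Day 28. 28 + 23 = 51 and 28 + 37 = 65. These days lie outside the Week 4 window (23–43) but inside Week 8 (Days 44–71), so they affect by-visit summaries and not the endpoint.

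Counting last dose from the SAP target day (85 or 29) shifts these ranges by one day and changes nothing.

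**5. Cohort 4–9 extension visits.** Their Week 8 and Week 12 visits belong to the extension (Protocol 3.1.3). With no cohort split in Table 7, these records can enter the Week 4 to Week 12 summaries of SAP 13.2.3, which Section 4 leaves to another SAP. Protocol 8.3.6 asks for these proportions at Week 4 in all cohorts and at Week 12 in Cohorts 1–3 only.

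**6. Size of one substitution.** In a cohort of 5, one participant is 1/5 = 20 percentage points. For example, 2/5 = 40% (exact 95% CI 5.3–85.3%) becomes 3/5 = 60% (14.7–94.7%). In a cohort of 10 it is 10 points.

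**The case against.** Much can be said for the plan, and several stronger readings fail.

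- **A reader might infer that a participant who skipped the endpoint visit altogether can be credited with a value from a higher extension dose.** The documents do not support that, because extension entry requires completing Visit 6 or Visit 4. The remaining gap is an attended visit without a usable A4, which SAP 9.5 covers as partially completed. A glucocorticoid change is a weak route for the same reason: without an A4 result the adjustment algorithm is not triggered.
- **A reader might infer that everyone who stops at Week 12 supplies an off-drug A4.** The follow-up is a telephone call, and samples are exceptional.
- **A reader might infer that planned follow-up can replace the Cohort 4–9 endpoint.** Days 51–65 miss the Week 4 window.
- **A reader might take the Week 96 limit as proof that the same limit was forgotten elsewhere.** Week 96 is the last scheduled visit row and has no next midpoint, so the difference proves nothing.
- **A reader might call every off-drug value an error.** SAP 13.1 labels the secondary estimands as treatment policy, and values after early discontinuation fit that label. It does not explain samples taken after planned completion or on a changed extension dose.

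It can also be argued that a sample near last dose + 30 belongs naturally under Follow-up, since Days 107–121 are within 7 days of that target and 22–36 days from Day 85. That is probably the intent. But the row has no bounds and no precedence, so the text does not secure it. The Section 4 statement on the extension sets scope; it does not cut off the windows. Extension safety laboratories do not name A4 (Protocol Appendices 2 and 4, note 3), so they matter for A4 only if it is also drawn.

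**Conclusion.** The point holds in a limited form. Followed as written, SAP 9.5 and Table 7 can label a sample taken after an extension-period tildacerfont change, or after planned end of treatment, as the endpoint value. That would displace the non-response the SAP otherwise requires. Week 12 in Cohorts 1–3 is more exposed than Week 4 in Cohorts 4–9.

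The number affected is likely small. The documents give no rate of missing endpoint A4, so it cannot be estimated. The 20-point figure is the effect of one participant in a cohort of 5, not an expected bias. The endpoints concerned are secondary and exploratory and reported descriptively; the adverse-event primary endpoint does not depend on these windows.

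This rests on three assumptions: last dose falls near Day 84 or Day 28 for completers; unscheduled samples include A4; and no cut-off is set in SAP 9.2.1 (same-cohort re-enrolment), whose text was not available to me.

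**What to change.** Amend SAP 9.5 and Table 7 as follows.

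1. **Participants who enter the extension:** admit to treatment-period visits only records collected up to and including the extension-entry visit (Week 12 for Cohorts 1–3, Week 4 for Cohorts 4–9) and before any extension-period tildacerfont change. This also keeps Cohort 4–9 extension visits out of the Week 8 and Week 12 summaries.
2. **Participants who complete treatment and do not continue:** end the endpoint window at last dose + 3 days, the allowance already used for Week 96.
3. **Follow-up:** give the row bounds of last dose + 23 to + 37 days, taking precedence over the on-treatment windows.
4. **Early discontinuation:** state whether off-drug values are kept under the treatment-policy strategy. Either choice is defensible if declared before lock.

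Extension entry is the better boundary for those who continue. Their dosing does not stop, and SAP Section 15 says the last dose date of the 12-week period would have to be assumed. For those who do not continue, the plan already relies on last dose for the Follow-up target and the treatment-emergent definition; any assumed date should be documented.

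The cost is SAP wording and a revised visit derivation, with no new data. The downside is that a few endpoint values become missing and are scored as non-response.

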**Table 7 Analysis Visit Windows**

Protocol Specified Visit Number	Analysis Visit	Target Study Day	Start (days)	Stop (days)
1	Screening	-15	low	-1
2	Day 1	1	1	8
	Day 2	2		
	Day 8	8		
	Day 14	14		
3	Week 2	15	9	22
4	Week 4	29	23	43
5	Week 8	57	44	71
6	Week 12	85	72	127
7	Week 24	169	128	211
8	Week 36	253	212	295
9	Week 48	337	296	421
10	Week 60	421	341	501
11	Week 72	505	411	599
12	Week 84	589	481	697
13	Week 96	673	551	Last Dose Date + 3 days
7	Follow-up	Last Dose Date + 30		

## 10 GENERAL CONSIDERATIONS

### 10.1 Adjustments for Covariates

Due to the limited size of the sample and the exploratory nature of this trial, adjustments for covariates may introduce potential biases or limitations. Therefore, summaries of secondary and exploratory efficacy endpoints may be generated without incorporating covariates such as age group, gender, and pubertal status. The trends in these covariates may be evaluated in summaries by subgroup as specified in supportive sections of the efficacy endpoints ([Sections 13.1.1.3](#) and [13.2](#)).

### 10.2 Handling Dropouts or Missing Data

Every effort will be made by the Sponsor to ensure completeness of data collection. Missing data will not be imputed unless otherwise specified.

#### 10.2.1 Handling of Laboratory Data

For non-PK laboratory values that are continuous in nature and either above or below the respective quantitation limits (X), the following imputations will be made for the purposes of summarization:

- If a value is reported as ‘< X’, then the imputed value will be X/2
- If a value is listed as =X, then the imputed value will be X
- If value is reported as ‘> X’, then the imputed value will be X+1

#### 10.2.2 Handling of Safety Data

##### 10.2.2.1 Adverse Events

In the event that the time of AE onset (before or after intake of study drug) cannot be determined and if an AE is treatment-emergent because of a partial onset date, the event will be counted as a TEAE. Adverse events with incomplete onset and end dates will have their dates imputed and then treatment-emergent status will be evaluated.

Incomplete adverse event onset date/time:

- If day is missing:
  - If month and year are the same as the month and year of first study drug exposure, then impute to the date of first study drug exposure.
  - Else if day is missing and year or month is not the same as the year and month of first study drug exposure, then impute as Day 1 of the month.
- If month is missing:
  - If year is the same as the year of first study drug exposure, then impute to the date of first study drug exposure.
  - Else if year is different from the year of first study drug exposure, then impute as January 1.

- If year is missing, then impute to the date of first study drug exposure.
- If imputed start date is after AE end date, then impute the start date to the AE end date.

Incomplete adverse event end date/time:

- If only have a YEAR, impute as December 31.
- Else if only have YEAR and MONTH, then impute to last day of the month.
- Otherwise missing, no imputation.

If severity or relationship of an AE to study drug is not recorded, the severity or relationship will be imputed as “severe” or relationship as “possibly related,” for analysis purposes. All efforts will be made to ensure no missing severity or relationship of an AE to study drug prior to database lock finalization.

#### *10.2.2.2 Concomitant Medications*

If the start date of a medication is missing, the medication will be considered to have started prior to the study. Such a medication may also be considered concomitant, depending on the stop date or lack thereof. If the stop date of a concomitant medication is missing, then the medication will be treated as ongoing. If the start date of a medication is missing, the stop date will be used to determine whether it is concomitant. Medications with other incomplete start dates or end dates will be imputed as follows:

Incomplete medication start date/time:

- If only have a YEAR, impute as January 1.
- Else if only have YEAR and MONTH, impute as Day 1 of month.
- Otherwise missing, no imputation. Incomplete medication end date/time:
- If only have a YEAR, impute as December 31.
- Else if only have YEAR and MONTH, then impute to last day of the month.
- Otherwise missing, no imputation.

### **10.3 Primary Analyses**

The primary analyses will be conducted when all subjects complete Week 12 of study treatment and the study and the data has been frozen for analysis.

### **10.4 Multicenter Considerations**

This is a multicenter trial in the United States. Data from all study centers will be pooled for efficacy and safety analyses. Because the number of subjects at each center is likely to be small, no analyses will be performed by the center.

### **10.5 Multiple Comparisons, Multiplicity**

This Phase II study is exploratory in nature and no adjustment for multiplicity is planned. The existence of multiplicity is acknowledged, and interpretation of the secondary and exploratory results will be interpreted with caution.

## **10.6 Active-Control Studies**

Since all subjects will receive open-label study drug, there is no placebo group to serve as a comparator in this study.

## **10.7 Examination of Subgroups**

Subjects will be categorized into the following common subgroups for the purposes of evaluating the pharmacodynamic endpoints. Due to the small sample size, subgroups will be summarized descriptively in place of subgroup analyses.

- Baseline A4 ( $\leq$  ULN;  $>$  ULN)
- Sex (Male, Female)

# **11 STUDY SUBJECTS**

## **11.1 Subject Enrollment and Disposition**

Screening and disposition will be summarized study-wide and by cohort.

Enrollment and disposition will be summarized by cohort and overall. Dose discontinuations and reasons for study drug discontinuation will be listed and summary tables.

A subject listing with enrollment, disposition, dose, dose discontinuations, site ID, date of informed consent, and reason for screen failure for subjects who were screened but not enrolled will be generated.

A separate listing will display subjects who are excluded from SAF and PD analysis sets, along with reasons for the exclusions.

